5.6 Randomisation

To determine whether altering muscle substrate availability impacts upon metabolic health, participants will be asked to take an oral supplement 4 times a day during the 2-day forearm immobilization period. Participants will be randomly allocated to receive a supplement containing either acipimox, salbutamol, or a placebo containing only cellulose microcrystalline.

Randomisation will be via a computer generated randomisation schedule provided by the involved statistician ([name]), and held in a folder in his office in Richards Building (St Luke's Campus). A secure Excel document of the randomization schedule (treatment A, B, or C) will be accessible by all members of the study team, including [name] and the Pharmacy contact. Supplementation compliance will be monitored via self-reported supplement intake diaries, and content counting from returned supplement containers.

The arm-to-be-immobilized will be counterbalanced between the dominant and non-dominant arm.

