Secondary	Determine the impact of reduced muscle lipid availability and increased glycolytic flux on muscle protein synthesis, and forearm nutrient balance during short-term forearm immobilization in healthy volunteers	Postabsorptive and postprandial muscle protein synthesis Forearm branched-chain amino acid and fatty acid balance Forearm volume
Medication to be administered	Administered during the 2-day forearm immobilization period: Acipimox OR Salbutamol OR Placebo	
Formulation, Dose, Route of Administration	Acipimox, 250 mg, 4 times daily, oral administration Salbutamol, 4 mg, 4 times daily, oral administration	

	Placebo, no active ingredients, 4 times daily, oral administration
CTIMP? (yes/no)	No (confirmation from MHRA is included in this application)

iv. FUNDING AND SUPPORT IN KIND

FUNDER(S)	FINANCIAL AND NON FINANCIAL SUPPORT GIVEN
Wellcome Trust [name]	Sir Henry Wellcome Postdoctoral Fellowship to [name]
Sport and Health Sciences College of Life and Environmental Sciences University of Exeter [name]	

v. ROLE OF TRIAL SPONSOR AND FUNDER

This study is funded by a 4-year Sir Henry Wellcome Postdoctoral Fellowship to [name]. [name] and [name] were responsible for the study design. The University of Exeter acts as a sponsor for this study. [name] will be responsible for data collection and analysis, decision to publish, and preparation of manuscript(s).

The UK Policy Framework for Health & Social Care and Medicines for Human Use (Clinical Trials) Regulations and Amendment Regulations 2006 require that all health-related research has a sponsor and sets out the responsibilities of the sponsor. The sponsor takes overall responsibility for the initiation, management and financing (or arranging the financing) of the research and must satisfy itself that appropriate arrangements are in place for management, monitoring and reporting of research activity. It is recognised that the sponsor can delegate specific responsibilities to any other individual or organisation that is willing and able to accept them. However, any delegation of responsibilities to another party should be formally agreed and documented by the sponsor.

vii. Protocol contributors

[name] – protocol development and scientific critique

[name] – protocol development and scientific critique

[name] (medical collaborator) – protocol development and risk assessment

[name] – Lead statistician

[figure not shown]

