5 TRIAL SETTING, DESIGN, AND PROCEDURES

This study is a randomized, double-blind, placebo-controlled trial with a parallel group design in healthy young volunteers. This study will determine the impact of pharmacological manipulation of substrate availability on insulin sensitivity, and anabolic sensitivity during 2 days of forearm immobilization. This study comprises of four study visits, depicted in the study schematic on Page 11 and described in detail in paragraph 5.5 below.

This study is a single-centre study, with all visits performed in the Clinical Research Facility at the Royal Devon & Exeter NHS Foundation Trust. Dispensing of the drugs will be performed by the Clinical Trials Pharmacy at the Royal Devon & Exeter hospital in Exeter.

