- At t = 2.5 h, a hyperinsulinaemic-euglycaemic-hyperaminoacidaemic clamp will be started. For this, insulin will be infused at a rate of 50 mU·m⁻²·min⁻¹, and a simultaneous infusion of 20% glucose will be started to maintain euglycaemia at 5.0 mmol·L⁻¹. A 0.3% potassium chloride solution will be infused in the (to be) immobilized arm at a rate of 1 ml/kg body weight/h during the 3-h clamp to maintain plasma potassium concentrations [25]. Hyperaminoacidaemia will be induced by infusion of an amino acid solution (Primene 10%, Baxter) at BCAA concentrations of 700 μmol·L⁻¹. This concentration was chosen as it is the average postprandial BCAA concentration following mixed meal ingestion in the pilot study. Primene will be 7% enriched with L-[ring-²H₅]-phenylalanine to prevent a decrease in plasma enrichments with Primene infusion. Measurements of blood glucose (Yellow Springs Instruments; every 5 min) and BCAA (spectrophotometric assay, [26]; every 20 min) concentrations will be performed at the bedside, and the infusion rate of glucose and amino acids adjusted accordingly to maintain steady state. Throughout the entire 5.5 h infusion period, repeated arterialised-venous (AV) and deep-venous (V) blood samples will be taken in order to calculate forearm AV-V balance of glucose (i.e. insulin sensitivity), amino acids, and free fatty acids using the Fick principle [27]. Prior to every blood sample, brachial artery blood flow will be measured using Doppler ultrasound.

- After 2 hours of the 3h clamp, a single dose of 10 mg metoclopramide hydrochloride will be administered intravenously in an antecubital elbow cannula, to prevent potential gastrointestinal issues during the final hour of the clamp.
- Following the 3 h clamp, infusion of insulin, amino acids and stable isotope amino acids will be stopped while infusion of glucose will be decreased in a stepwise manner based on blood glucose concentrations. The last 30 min of the clamp will be used to calculate the mean glucose infusion rate (GIR) and mean amino acid infusion rate. Participants will be monitored for minimally 20 min following cessation of the glucose infusion before they are allowed to leave the laboratory.

Forearm casting and drug dispensing (visit 3; to take place between 7 and 28 days after visit 2):

- In the morning at 7:30 AM, participants will visit the Clinical Research Facility at the Royal Devon & Exeter NHS Foundation Trust in an overnight fasted state.

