5.7 Blinding

The trial products (i.e. Acipimox, Salbutamol, or placebo) will be received by the Clinical Trials Pharmacy in a distinguishable manner. They will be handled only by unblinded personnel until repackaged in an opaque container. Each container will be labelled with a unique pack ID to identify each pack and its content. The treatment will be prescribed by [name], and dispensed to the participant by the Pharmacy. Participants will be instructed not to discuss the product they receive with anyone inside or outside the research team.

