8.2 Recording and reporting of adverse events

Any adverse effects noted will be recorded in the adverse event log and reported to the CI and the study sponsors as per standard University of Exeter sponsor protocols (please refer to Letter from sponsor, included in this application). The CI will have a professional obligation to closely monitor participants and in the event of an adverse event being identified, follow established clinical treatment or referral protocols.

Participants will be instructed to contact the study team immediately should they feel unwell, and will be provided with contact numbers for contacting the team directly. Participants will be issued with a

card indicating their participation. This card will also identify their allocation code and identify reasons and who to contact should breaking the allocation code become necessary.

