8.3 Emergency unblinding

The investigators may identify the treatment for each participant through sealed envelopes in the event of a medical emergency or SAE when treatment is dependent on knowledge of the actual drug received. The CI will be notified if the treatment code for a participant is broken, and the date and the reason(s) for breaking the blind will be noted in the CRF in a timely manner (notification of Sponsor immediately as practicable by phone or fax, followed by a written narrative of the event within 24 hours, as described above). Emergency unblinding will be carried out by the medical collaborator ([name]). He will at all times have access to the sealed list with participant names and treatment allocation.

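### Section 5.6 opens the A/B/C randomisation list to the whole study team; if each letter stands for one drug, a single decode that reaches the bedside could expose a whole arm instead of one participant

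*Combined protocol and SAP*

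**What the plan says.** Section 5 gives the design: "This study is a randomized, double-blind, placebo-controlled trial with a parallel group design in healthy young volunteers". On custody, section 5.6 says the statistician's computer-generated schedule is "held in a folder in his office", and the next sentence adds: "A secure Excel document of the randomization schedule (treatment A, B, or C) will be accessible by all members of the study team". The Pharmacy contact is among those listed as having access.

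Section 5.7 has unblinded personnel handle the products until they are repackaged in opaque containers, and continues: "Each container will be labelled with a unique pack ID to identify each pack and its content". It sets no limit on who may see the letter list and does not say which team roles are blinded.

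Three other places bear on the point:

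- Section 8.2 gives each participant a card: "This card will also identify their allocation code". It does not say whether that code is the letter, the pack ID or something else.
- Section 8.3 assigns emergency unblinding to the medical collaborator: "He will at all times have access to the sealed list with participant names and treatment allocation". The same section also lets investigators identify a participant's treatment through sealed envelopes.
- Section v says of one named person that they "will be responsible for data collection and analysis".

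**The concern.** A group letter hides the drug name but shows which participants share a treatment. Anyone with the list can carry what is learned about one participant over to everyone with the same letter, and can pool weak clues across an arm. A code unique to each participant allows neither.

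Bedside blinding matters here because part of the primary outcome depends on an operator. Forearm glucose uptake is calculated from arteriovenous differences and blood flow, and section 5.5 says: "Prior to every blood sample, brachial artery blood flow will be measured using Doppler ultrasound". The bedside team also adjusts the glucose infusion during the clamp. As written, the person responsible for both data collection and analysis has the list too.

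There is a second issue at enrolment. If the file shows the whole schedule, staff who screen and enrol can see the letter that the next participant will receive. Allocation is then not fully concealed, even while the meaning of the letters is unknown.

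**Working it through.** **Inputs.** Section 9.1: 12 completers per group, up to 20% dropout, 15 recruited per group, 45 in total. Section 5.6: three letters. Section 3: side effects in about 2 in 10 on acipimox and 1 in 10 on salbutamol.

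**The plan's group sizes reproduce.** A two-sided two-sample t-test at 5% with standardised effect 1.23 needs 12 per group (power 82.1%; 11 per group gives 78.3%). Allowing for dropout, 12 / (1 − 0.20) = 15 per group, and 3 × 15 = 45. Completers number 3 × 12 = 36.

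**Participants identified by one decode**, assuming a fixed letter-to-drug link and a decode that is correct and known to the team:

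| Coding seen by the team | As recruited | Planned completers |
|---|---|---|
| Shared letters | 15 of 45 (33%) | 12 of 36 (33%) |
| Participant-specific pack IDs | 1 of 45 (2%) | 1 of 36 (3%) |

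A second decoded letter would give the third by elimination, and so all participants.

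**How many could still be affected at the bedside.** Tests already done cannot be changed, so only same-arm participants not yet tested count. With N participants in random order, n per arm, and a decode at the k-th tested, the expected number is (N − k) × (n − 1) / (N − 1).

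- As recruited, decode at the first participant: 44 × 14/44 = 14.0, the maximum. At the 23rd: 22 × 14/44 = 7.0.
- Completers only, decode at the first: 35 × 11/35 = 11.0, the maximum. At the 18th: 18 × 11/35 = 5.7.
- With pack IDs: 0 at any k.

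The mid-trial values are illustrations. The documents do not say when a decode would occur.

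**How often a clue might arise.** With 15 per group and independence between participants, the chance of at least one participant with side effects is 1 − 0.8^15 = 96.5% on acipimox and 1 − 0.9^15 = 79.4% on salbutamol. These are chances of a clue, not of a decode. The rates cover all the mild-moderate effects listed, including non-specific ones such as headache and nausea.

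**Search for a limiting provision.** Section 5.7 controls product handling and container labels, and 8.3 controls the sealed list. Neither limits who may open the A/B/C file, puts participant-specific codes in it, or withholds future allocations.

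**The case against.** The strongest reply is that this is an ordinary coded arrangement: a master in the statistician's office, a working copy in letters, and product identity kept in the Pharmacy. That stands in part. A reader might infer that the two custody sentences in 5.6 contradict each other, but the text does not support this. The parenthesis naming the letters marks the shared file as a coded copy, which can coexist with an office-held master. A reader might also infer that the shared file unblinds the team. It does not, because no drug name is in it.

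A second reply is that an emergency break need not reach the assessors. Section 8.3 gives the break to the medical collaborator and has the chief investigator told that it happened, with date and reasons recorded. It does not say that the drug identity goes to the bedside team. So it cannot be asserted that one break removes blinding for an arm. The route is not closed, however, because the same section also allows investigators to identify treatment from the envelopes.

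Third, a recognised side effect points to that participant's drug under any coding system. That is true. Pack IDs prevent only the spread to others, which is the whole of the point made here.

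Finally, the fixed letter-to-drug link and a file listing the full schedule are both assumptions. Each is a natural reading, and neither is stated.

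**Conclusion.** The point holds in a conditional form. Team-wide access to the letter list is explicit, and nothing elsewhere limits it. If each letter means one drug throughout, and if a correct decode reaches the bedside team, the number identified rises from one participant to up to 15 of 45 (12 of 36 completers). Of these, at most 14 others (11 among completers) could still be affected at the bedside, and fewer the later it happens. If the file lists the full schedule, allocation concealment at enrolment is also weaker than it needs to be.

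The documents give no basis for a bias size, a false-positive rate or the probability of a decode, and none is claimed. A reader who infers that the trial is unblinded, or that its result would be invalid, goes beyond the text. This is a free improvement to a declared safeguard.

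**What to change.** In 5.6, limit the schedule, including the A/B/C list, to those who need it. For example:

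> The schedule and any list of group letters are held only by the statistician and the unblinded Clinical Trials Pharmacy staff. All other team members, including the prescriber, identify assignments only by participant-specific pack ID. The statistician releases group labels for analysis after the last visit 4.

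In 5.7, state that the pack ID links to content only through the list held by the statistician and Pharmacy, that it shows no group letter or product, and which roles are blinded. The present sentence, which says the ID identifies the pack and its content, leaves this open. In 8.2, state that the allocation code on the card is that pack ID; this is a clarification, since nothing shows that the letter is meant. Leave the sealed emergency access in 8.3 unchanged.

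The cost is a change of file permissions and a few sentences. Sample size, visits, products and emergency unblinding are unaffected.

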- A fiberglass forearm cast (randomized between dominant and non-dominant arm) will be applied from below the elbow to approximately 2-3 cm below the finger tips, to immobilize the wrist. Participants will be given a sling to wear at all times, except for during sleeping and showering. A waterproof cover will be provided to cover the cast during showering.
- Participants will then receive the food products for the controlled diet, which they will consume during the 2 days of forearm immobilization. Participants will be fed in energy balance, with energy requirements calculated as basal metabolic rate (Henry equations) times an activity factor (IPAQ questionnaire). The diet consists of 1.2 g/kg body weight/day protein (approx. 10-15 en%), 50-55 en% carbohydrate, and 35 en% fat. The diet will be composed of three main meals (i.e. breakfast, lunch, dinner) and snacks, and will contain normal food products. A food diary including recipes for the evening meals will be given, and the entire diet will be explained.
- Lastly, participants will visit the Clinical Trials Pharmacy at RD&E to collect their allocated treatment. Instructions on the times and way to ingest the treatment is provided by trained staff, and a treatment log will be provided. The first out of eight doses will be taken.
- Participants will be sent home, and will return to the CRF two days later for visit 4.

Post-immobilization metabolic test day (visit 4):

- In the morning at 8 AM, participants will visit the Clinical Research Facility at the Royal Devon & Exeter NHS Foundation Trust in an overnight fasted state.
- The metabolic test day will be repeated.
- The fiberglass cast will be removed.

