9 STATISTICS AND DATA ANALYSIS

9.1 Sample size calculation

We have powered the study to detect a difference in forearm glucose uptake (primary outcome measure) between 1) Acipimox vs placebo, and 2) Salbutamol vs placebo. We have powered the study based on detecting differences in the change in forearm glucose uptake as measured during the hyperinsulinaemic-euglycaemic clamp, which is golden standard to measure insulin sensitivity. We have recently generated pilot data to demonstrate that forearm glucose uptake decreases by $13\pm 8\%$ (mean \pm SD) in response to mixed meal ingestion following 2 days of forearm immobilization. Based on our hypotheses, lowering lipid availability (via Acipimox) and stimulating glycolytic flux (via Salbutamol) will alleviate insulin resistance (i.e. prevent the decline in forearm glucose uptake). The following data were used to estimate the effect size, using $\alpha = 0.05$; power = 80%; significance = 5%:

- 1) Placebo ($-13\pm 8\%$) vs Acipimox ($0\pm 8\%$; preservation of forearm glucose uptake [14]. Effect size: 1.625. Required: $n=8$
- 2) Placebo ($-13\pm 8\%$) vs Salbutamol ($-4.3\pm 6\%$; 66% attenuation of decline in forearm glucose uptake by a beta2-agonist [28, 29]. Effect size: 1.23. Required: $n=12$

To have enough power for both comparisons, $n=12$ participants will be included in all groups (i.e. placebo, Acipimox, Salbutamol).

Thus, assuming a $\leq 20\%$ dropout rate (in our experience, similar immobilization studies do not exceed this drop-out rate when using healthy adults), we will recruit 45 healthy adults 18-40 years old, from both sexes, who will be split across 3 parallel groups (i.e. $n=15$ per group, ensuring completion of $n=12$ per group).

Sample size was calculated using G*Power 3.1.9.2.

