9.3.2 Primary outcome analysis

The primary outcome measure for this study is forearm glucose uptake, measured during the steady-state phase of a 3-h hyperinsulinaemic-euglycaemic-hyperaminoacidaemic clamp. A two-way ANOVA, with and treatment (placebo vs Acipimox vs Salbutamol) as between-subjects factor and time (pre vs post immobilization) as within-subjects factor. A Bonferroni post-hoc test will be used to locate individual differences.

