9.3.3 Secondary outcome analysis

Secondary outcome measures include postabsorptive and postprandial muscle protein synthesis, and forearm branched-chain amino acid and fatty acid balance. These data will be analysed in the same way as the primary outcome described above.

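### Cast arm (dominant or non-dominant) is allocated by design, but the plan does not say it is balanced within treatment groups and leaves it out of the primary and secondary models

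*Combined protocol and SAP*

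**What the plan says.** Cast arm appears twice as an allocated factor. Section 5.5 (visit 3) says: "A fiberglass forearm cast (randomized between dominant and non-dominant arm) will be applied". Section 5.6 says: "The arm-to-be-immobilized will be counterbalanced between the dominant and non-dominant arm". The drug allocation is described separately in 5.6: "Randomisation will be via a computer generated randomisation schedule provided by the involved statistician". No blocking or stratification is described, and nothing links the cast-arm allocation to the drug schedule.

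The primary model in 9.3.2 has "treatment (placebo vs Acipimox vs Salbutamol) as between-subjects factor and time (pre vs post immobilization) as within-subjects factor". Section 9.3.3 says of the secondary outcomes: "These data will be analysed in the same way as the primary outcome described above". Cast arm is in neither model.

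The quantity of interest is change. Section 9.1 says: "We have powered the study based on detecting differences in the change in forearm glucose uptake".

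**The concern.** A factor that is controlled at allocation would normally be carried into the analysis. Because each participant is compared with their own baseline, a constant difference between dominant and non-dominant arms drops out. A difference in the size of the decline does not: it is an arm-by-time effect, and the treatment-by-time test works on exactly that scale. Such an effect is conceivable, since casting the more-used arm may be a larger drop in activity, but the documents give no evidence on it.

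The consequence depends on what counterbalanced means here:

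- **Balanced within drug groups.** The arm effect cancels from the treatment contrast but stays in the residual. The reported standard error is then too wide and the test conservative.
- **Balanced only over the whole trial.** Drug groups can differ by chance in their number of dominant-arm casts, and that adds noise to the contrast.

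These are alternatives, not cumulative harms. With 12 completers per group and little spare power for salbutamol, a cheap gain in precision is worth having.

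**Working it through.** **Inputs from 9.1.** Placebo −13 (SD 8)%, acipimox 0 (SD 8)%, salbutamol −4.3 (SD 6)%; "power = 80%; significance = 5"%; 12 completers and 15 recruited per group. Sidedness is not stated.

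**Reproducing the plan's figures** (two-sample t-test, noncentral t, two-sided 5%):

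- Acipimox: d = 13/8 = 1.625, giving n = 8 per group (power 85.6%).
- Salbutamol: SD = √((8² + 6²)/2) = 7.07; d = 8.7/7.07 = 1.23, giving n = 12 per group (power 82.1%).
- 12/0.8 = 15 per group, and 3 × 15 = 45.

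All agree with the plan. A one-sided 5% test would give 6 and 9, so two-sided was evidently used. At 12 per group acipimox already has 96.7% power, so the salbutamol contrast is where precision matters.

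**Assumption.** D is the dominant vs non-dominant gap in the change, in percentage points, taken as equal in all groups. Total SD is held at 7.07, so the SD within an arm is √(7.07² − D²/4): 7.00 at D=2, 6.78 at D=4 and 5.83 at D=8.

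**Case 1: balanced within groups (6/6 of 12), salbutamol vs placebo, by simulation**

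| D | Power without term | Power with term | Type I error without term |
|---|---|---|---|
| 0 | 82% | 82% | 5% |
| 2 | 82% | 83% | 5% |
| 4 | 83% | 85% | 4% |
| 8 | 86% | 94% | 2% |

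The reason is visible at D=8. The true standard error of the contrast is 5.83 × √(2/12) = 2.38, while the unadjusted analysis reports about 2.90 on average, because the arm effect is still in its residual. At D=2 the gain is under half a point before rounding. At D=0 the term costs about 0.2 points of power.

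**Case 2: balanced only over the whole trial.** With 22 of 45 casts on the dominant arm and three groups of 15, the probability that a given pair of groups has a and b dominant-arm casts is C(15,a)·C(15,b)·C(15,22−a−b)/C(45,22). Summing over |a − b|:

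- at least 3: 36.7%
- at least 4: 20.6%
- at least 5: 10.3%

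With 12 completers per group (18 of 36 dominant), at least 3 has probability 31.4% and at least 5 has 6.8%.

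A 5-cast difference shifts the contrast by (5/15) × D = D/3: 0.7 points at D=2, 1.3 at D=4 and 2.7 at D=8, against the planned 8.7. The last two are 15% and 31% of that target.

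The unadjusted test remains valid here. With arms shuffled across 36 completers, type I error stays at about 5% at both D=4 and D=8, and the reported standard error (2.85 and 2.87) is close to the true one (2.89 and 2.92). The ordinary standard error already covers the chance imbalance.

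**The case against.** The strongest reply is that no benefit has been demonstrated. The documents give no dominance effect on the decline, and a gap of 8 points would be 62% (8/13) of the whole pilot decline of 13 points. For gaps up to 2 points the gain is negligible. That stands, and it is why the size is given as a range.

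A common D is also generous. Section 9.1 supposes that the drugs prevent most or all of the decline, so a gap in that decline would plausibly shrink with it. If the gap in the salbutamol group is scaled by 4.3/13 (an assumption), the gain falls to about 82% vs 83% at D=4 and 84% vs 88% at D=8. That also stands.

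Three stronger readings are tempting, and the documents do not support them.

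- A reader might infer that cast arm is not balanced within drug groups. The plan is silent, and counterbalanced is compatible with balance within groups.
- A reader might take randomised in 5.5 and counterbalanced in 5.6 as a contradiction. Random allocation to equal numbers is both. The wording needs aligning, but it is not proof of conflict.
- A reader might call the imbalance bias, or add it to the over-wide standard error. Chance imbalance is not bias in expectation. The over-wide standard error needs balance within groups, whereas sizeable chance imbalance needs its absence. Neither case raises the false-positive rate.

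**Conclusion.** The point holds as a minor one. Cast arm is a design factor, its balance within treatment groups is not stated, and every planned analysis omits it.

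If it is balanced within groups, omission costs nothing worth counting for D up to 2, about 2 points of power at D=4 and about 8 at D=8, with a conservative test. If it is balanced only overall, the test is sound but carries avoidable variance.

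These figures rest on an assumed D that is common to all groups, the SDs in 9.1, a two-sided 5% level for the single salbutamol contrast, and 12 completers per group. They do not show that the planned analysis is invalid or that the trial is underpowered.

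**What to change.** - **5.6:** generate cast arm and treatment in one schedule, balanced within each treatment group (7/8 of 15). Use the same wording in 5.5.
- **9.3.2 and 9.3.3:** prespecify cast arm as a between-subjects factor with its time interaction or, equivalently, as a factor in a model for change. It should be fixed in advance, because a term added after the results are seen is open to challenge.
- **5.5 (baseline test day):** the deep-venous sampling cannula is placed in the non-immobilised arm, while the objective concerns the effect of forearm immobilisation. Reconcile these passages so that it is clear which arm is sampled and which arm the factor codes.

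**Cost.** One line in the schedule, one model term and no new data. The term uses one error degree of freedom in the model for change. If D is zero, that is about 0.2 points of power with balance within groups, and about 2 points if balance is only overall, because the arm is then partly confounded with treatment. The 7/8 split may also drift with the allowed dropout of up to 20%, which the model term then handles.
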